#### **8.4.8. Adverse Events of Special Interest**

##### **8.4.8.1. Protocol-Defined Adverse Events of Special Interest that Require Reporting to Sponsor's Global PV**

For purposes of this protocol, the following are considered protocol-defined adverse events of special interest to be sent to the Sponsor's Global PV for evaluation: ophthalmic-related adverse events of at least moderate severity and severe hypersensitivity or anaphylactic reactions.

Hypersensitivity reactions will be monitored using the diagnostic criteria for anaphylaxis as outlined by the 2006 Joint National Institute of Allergy and Infectious Disease/Food Allergy and Anaphylaxis Network Second Symposium on Anaphylaxis ([Sampson et al 2006](#)). The clinical criteria for diagnosing anaphylaxis are provided in Section [12.1](#). In the event of suspected anaphylaxis, vital signs (including oxygen saturation and respiration rate) will be measured.

The process for reporting a protocol-defined adverse event of special interest is the same as that for reporting a serious adverse event (Section [8.4.6](#)), using the same Serious Adverse Event/Protocol-Defined Adverse Events of Special Interest Form. Protocol-defined adverse events of special interest to be reported to Global PV can be either serious or nonserious, according to the criteria outlined in Section [8.4.1](#). Protocol-defined adverse events of special interest that occur before IMP (and/or PFS) administration do not require reporting to Global PV.

Adverse events of special interest for pediatric participants are not listed in the Pediatric Investigation Plan or Pediatric Study Plan.

#### **8.4.9. Disease-Related Events or Outcomes not Qualifying as Adverse Events or Serious Adverse Events**

Disease state is an efficacy variable for this trial and should be captured on the eCRF; accordingly, disease-related manifestations should not be recorded as adverse events unless assessed as more severe than the participant's usual disease course. Disease manifestations that are more severe than the participant's usual course of disease and meet the criteria for a serious adverse event should be reported as a serious adverse event.

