### **7.4. Trial Stopping Rules**

There are no formal rules for early termination of the trial. During the conduct of the trial, serious adverse events will be reviewed as they are reported from the investigational centers to identify safety concerns.

The trial may be terminated by the Sponsor for any reason at any time. For example, the Sponsor should terminate the trial in the event of the following:

- new toxicological or pharmacological findings or safety issues that invalidate the earlier positive benefit-risk assessment
- discontinuation of the development of the IMP

If the whole trial or arms of the trial are stopped, the participants that are terminated early will be followed according to criteria outlined in Section [7.2](#).

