## **8.4. Adverse Events and Serious Adverse Events**

### **8.4.1. Definitions of Adverse Events and Serious Adverse Events**

#### **8.4.1.1. Adverse Events**

Adverse events are categorized according to ICH guidelines and adverse device effects are categorized and classified according to ISO standard 14155. The procedures for device deficiencies that are not associated with an adverse event, as well as those that are associated with an adverse event or that have the potential to cause a serious adverse event, are described in Section 8.6.

An adverse event is any untoward medical occurrence in a participant administered a pharmaceutical product and which does not necessarily have a causal relationship with this treatment.

An adverse event can, therefore, be any unfavorable and unintended physical sign, symptom, or laboratory parameter that develops or worsens in severity during the course of this trial, or significant worsening of the disease under study, or of any concurrent disease, whether or not considered related to fremanezumab.

Accordingly, an adverse event can include any of the following:

- a new condition or the worsening of a preexisting condition
- intercurrent illnesses
- physical injuries and the mechanism that caused the injury
- events possibly related to concomitant medication
- drug/drug or drug/device interactions
- events occurring during diagnostic procedures or during any washout phase of this trial
- laboratory or diagnostic test abnormalities (note: Abnormal laboratory or diagnostic test results at the screening visit that preclude a participant from entering the trial or receiving trial treatment are not considered adverse events)

Worsening of the disease under study that occurs during the trial that is not typical of the participant's daily symptoms or leads to the participant's discontinuation will be considered an adverse event. Stable chronic conditions (such as arthritis) that are present before trial entry and do not worsen during this trial will not be considered adverse events.

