Migraine exacerbations, including acute headache, requiring headache medications will be collected as part of the efficacy assessment in this trial. Migraine exacerbations (including acute headache) should be recorded as an adverse event only if the presentation and/or outcome is more severe than would typically be expected from the normal course of the disease in a particular participant or if they are severe enough to require hospitalization of the participant, in which case they are recorded as serious adverse events.

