#### **8.4.1.2. Serious Adverse Events**

A serious adverse event is an adverse event occurring at any dose that results in any of the following outcomes or actions:

- results in death
- is a life-threatening adverse event (ie, the participant was at risk of death at the time of the event); it does not refer to an event which hypothetically might have caused death if it were more severe
- requires inpatient hospitalization or prolongation of existing hospitalization, which means that hospital inpatient admission or prolongation of hospital stay were required for treatment of an adverse event, or that they occurred as a consequence of the event

Hospitalizations scheduled before the participant signed the ICF will not be considered serious adverse events, unless there was worsening of the preexisting condition during the participant's participation in this trial.

- results in persistent or significant disability/incapacity (refers to a substantial disruption of one's ability to conduct normal life functions)
- is a congenital anomaly/birth defect
- an important medical event that may not result in death, be life-threatening, or require hospitalization, but may jeopardize the participant and may require medical intervention to prevent one of the outcomes listed in this definition

Examples of such events are intensive treatment in an emergency room or at home for allergic bronchospasm; blood dyscrasias or convulsions that do not result in hospitalization; or liver injury that meets the criteria for Hy's Law; or the development of drug dependency or drug abuse. Note: Any suspected transmission of an infectious agent via a medicinal product is considered an important medical event.

An adverse event that does not meet any of the criteria for seriousness listed above will be regarded as a nonserious adverse event.

See Section [12.2](#) for guidance regarding monitoring participants with elevated liver function tests.

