#### **8.4.6. Reporting of Serious Adverse Events**

To satisfy regulatory requirements, the Investigator must report all serious adverse events that occur during the trial, regardless of the judgment of relationship to administration of the IMP (and/or PFS), to the Sponsor except for serious adverse events listed in Section [8.4.9](#). The Investigator must report the event within 24 hours of learning about it. Completing the Serious Adverse Event Form and reporting the event must not be delayed, even if not all the information is available.

The Serious Adverse Event Form should be sent to the Local Safety Officer (LSO) or designee (as applicable, for eg, a contract research organization [CRO]) in a country without a Sponsor LSO; the LSO will forward the report to the Sponsor's Global PV.

Each report of a serious adverse event will be reviewed and evaluated by the Investigator and the Sponsor to assess the nature of the event and the relationship of the event to the IMP (and/or PFS), trial procedures, and to underlying disease.

The Investigator should forward additional information (follow-up) about any serious adverse event unavailable at the initial reporting within 24 hours of when it becomes known, following the same process as for the initial report.

The process for serious adverse device effect reporting to Global PV is the same as for serious adverse event reporting.

The following information should be provided to record the event accurately and completely:

- trial number
- Investigator and investigational center identification
- participant number
- onset date and detailed description of adverse event

- Investigator's assessment of the relationship of the adverse event to the IMP (no reasonable possibility, reasonable possibility)

Additional information includes:

- age and sex of participant
- date of first dose of IMP
- date and amount of last administered dose of IMP
- action taken
- outcome, if known
- severity
- explanation of assessment of relatedness
- concomitant medication (including doses, routes of administration, and regimens) and treatment of the event
- pertinent laboratory or other diagnostic test data
- medical history
- results of dechallenge/rechallenge, if known
- for an adverse event resulting in death
  - cause of death (whether or not the death was related to IMP)
  - autopsy findings (if available)

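### Protocol Sections 8.4.1.1 and 8.4.9 give opposite recording rules for a migraine admission within the child's usual course, and for such worsening that leads to discontinuation

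*Protocol*

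**What the plan says.** Four parts of the protocol bear on whether a disease event is recorded and reported.

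- **Section 8.4.1.1, migraine exacerbations.** The first trigger is an exacerbation "more severe than would typically be expected from the normal course of the disease in a particular participant", which makes it an adverse event (AE). The second trigger reads: "or if they are severe enough to require hospitalization of the participant, in which case they are recorded as serious adverse events". The two triggers are alternatives.
- **Section 8.4.1.1, worsening of disease.** "Worsening of the disease under study that occurs during the trial that is not typical of" the participant's daily symptoms is an AE, and so is worsening that leads to discontinuation. These too are alternatives.
- **Section 8.4.9.** Because disease state is an efficacy variable, "disease-related manifestations should not be recorded as adverse events unless assessed as more severe than" the participant's usual course. Manifestations that exceed the participant's "usual course of disease and meet the criteria for a serious adverse event should be reported as a serious adverse event". This section has no separate trigger for hospitalisation or discontinuation. The Amendment 09 change table lists it as new, for alignment with a template.
- **Section 8.4.6.** All SAEs go to the Sponsor within 24 hours, "except for serious adverse events listed in Section" 8.4.9.

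Section 8.4.1.2 lists among the seriousness criteria an event that "requires inpatient hospitalization or prolongation of existing hospitalization". Section 4.1.2 says there is no data monitoring committee. Section 7.4 sets no formal rules for early termination and says that "serious adverse events will be reviewed as they are reported from the investigational centers to identify safety concerns".

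**The concern.** Two sites could treat the same admission differently, each following the protocol. Consider a child who was admitted for migraine before the trial and is admitted again with an attack of the same severity. A site reading 8.4.1.1 enters an SAE. A site reading 8.4.9 can conclude that nothing exceeds the usual course and enter no AE. The documents do not say which section governs, and SAP Section 8.4 summarises whatever was recorded without settling it.

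An event left off the AE page does not reach the SAE review described in Section 7.4, the SAE tables, or the tables of withdrawal due to AEs. Nor do the documents describe another dedicated place for it. Section 8.4.9 rests on disease state being captured as efficacy data, but the diary questions in SAP Appendix A and the PedMIDAS items in Appendix C do not ask about admission, and Section 8.12 says that resource use is not evaluated. The protocol also gives no criterion for judging whether an admission exceeds the usual course.

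**Working it through.** The plan states no figure to reproduce. The check is to run each combination of facts through both rules.

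**Hospitalisation**

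| Admitted? | Worse than usual? | 8.4.1.1 | 8.4.9 | Agree? |
|---|---|---|---|---|
| Yes | Yes | SAE | SAE | Yes |
| Yes | No | SAE | Not recorded | **No** |
| No | Yes | AE | AE | Yes |
| No | No | Not recorded | Not recorded | Yes |

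The rules differ in exactly one of the four cases, because 8.4.1.1 joins its triggers with *or* while 8.4.9 makes exceeding the usual course a condition in every case.

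**Discontinuation**

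The structure is the same. Worsening that leads to discontinuation and exceeds the usual course is an AE under both sections. Worsening that leads to discontinuation but is judged to be within the usual course is an AE under 8.4.1.1 and is not recorded under 8.4.9.

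**Reporting**

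Section 8.4.6 excepts SAEs listed in 8.4.9. Section 8.4.9 contains no list, and its one sentence on SAEs tells sites to report. The exception therefore has no defined content. It may be read as covering usual-course admissions or as covering nothing.

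**Who is exposed**

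Inputs: 180 randomised as of 18 September 2023 (Amendment 09 details) and about 278 planned, 139 per group (Section 9.8).

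- Share randomised before 8.4.9 was added: 180 / 278 = 65%.
- Remaining: 278 − 180 = 98, or 98 / 2 = 49 per group.

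Some of the 180 may still have been on study when the amendment took effect, so 98 is an approximate count of those exposed to the new text.

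**Number of events**

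The documents give no rate of migraine admission, so the count cannot be computed. As an illustration only, assume that 1% to 3% of participants have any migraine admission over the 12 weeks:

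- among 49 per group: 0.01 × 49 = 0.5 to 0.03 × 49 = 1.5;
- among all 139 per group: 0.01 × 139 = 1.4 to 0.03 × 139 = 4.2.

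Under that assumption these are ceilings. They count every migraine admission, whereas only those judged to be within the usual course are in dispute.

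**The case against.** The best reply is that the specific rule should govern the general one. Section 8.4.1.1 names migraine exacerbations and hospitalisation; 8.4.9 is template text that mentions neither. Its SAE sentence states when to report and does not contain the word *only*. An investigator may also reasonably regard any admission, or any worsening that ends participation, as more than the usual course, and the sections then agree. This narrows the problem and explains why many sites would record the event. It does not remove it. The preceding sentence of 8.4.9 does bar recording unless the event is worse than usual, 8.4.1.1 treats admission and severity as separate conditions, and nothing states an order of precedence. The Safety Monitoring Plan, cited under Figure 2, may say more, but it is not among the documents.

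Review of SAEs is also not the only safeguard. Under Section 7.2 the Trial Leader is told of participants being considered for withdrawal due to AEs, Section 8.4.8.1 expedites events of special interest, and Section 8.3.3 sends ECG alerts to the Sponsor. This is correct, but none of these routes is directed at an admission that was never recorded as an AE.

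Two stronger readings are tempting. A reader might infer that 8.4.1.2 by itself makes every inpatient admission an SAE. It does not: it applies to events that are already AEs and excludes admissions scheduled before consent, so the conflict rests on 8.4.1.1. A reader might also infer that 8.4.6 plainly exempts these admissions from reporting. With no list in 8.4.9, the text does not establish that.

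**Conclusion.** The contradiction is in the text and is narrow: one hospitalisation case and one parallel discontinuation case, with a reporting exception of unclear scope. The number of affected events is unknown, probably small, and limited mainly to participants on study after Amendment 09.

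A reader might go further and say that usual-course admissions are the likeliest disease-related SAE, that they are the events most likely to differ between groups, or that one to four SAEs per group turn on the wording. The documents give no frequencies to support the first two. The third would require an assumed rate, all 139 participants per group, and every admission falling within the usual course. Nor do the documents show bias between groups; in a double-blind trial, inconsistent site practice may only add noise.

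The point still merits correction. A site following 8.4.9 as written could leave a child's migraine admission off the SAE page, in a trial with no data monitoring committee whose stated ongoing check is review of reported SAEs. This conclusion does not depend on any assumed rate.

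**What to change.** 1. Reconcile 8.4.1.1, 8.4.6 and 8.4.9. Word 8.4.9 so that its usual-course exemption does not override the hospitalisation and discontinuation triggers in 8.4.1.1.
2. In 8.4.6, delete the exception that refers to 8.4.9, or define the events it covers.
3. Ask sites for any migraine hospitalisation not entered as an SAE, and any worsening leading to discontinuation not entered as an AE. Do this before database lock if that is still possible. The Note to File of 29 May 2025, appended to the SAP, says the analysis had been conducted, so it may be too late; in that case report the result of the query in the CSR.

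The cost is two wording changes, one site query and a few more SAE forms for expected migraine admissions.

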#### **8.4.10. Protocol Deviations Because of an Adverse Event**

If a participant experiences an adverse event or medical emergency, deviations from the protocol may be allowed on a case-by-case basis. To ensure participant safety, after the event has stabilized or treatment has been administered (or both), the Investigator or other physician in attendance must contact the Clinical Leader as soon as possible to discuss the situation. The Investigator, in consultation with the Sponsor, will decide whether the participant should continue to participate in the trial.

## 8.5. Pregnancy and Postpartum Information

Any female participant becoming pregnant during the trial will discontinue IMP (and/or PFS) and will be withdrawn from the trial.

All pregnancies of women participating in the trial and female partners of men participating in the trial, if applicable that occur during the trial or within at least 5 half-lives (ie, 6 months) or 180 days from last IMP dose, whichever is longer, are to be reported within 24 hours from Investigator awareness. The completed Pregnancy Form should be sent to the LSO/CRO (as applicable, for eg, a CRO in a country without a Sponsor LSO); the LSO will forward the report to the Sponsor's Global PV. The process for reporting a pregnancy is the same as that for reporting a serious adverse event but using the Pregnancy Form (Section 8.4.7).

The Investigator is not required to report participants who are found to be pregnant between screening and baseline, provided no protocol related procedures were applied.

Because there is lack of data on human teratogenicity, genotoxicity, fetotoxicity, or spermatoxicity for this IMP, female partners of men participating in the trial who become pregnant will be asked to sign an ICF. All female participants and female partners of men participating in the trial who become pregnant will be monitored for the outcome of the pregnancy (including spontaneous, elective, or voluntary abortion). If the pregnancy continues to term, the outcome (health of the infant up to 8 weeks of age), including details of birth and presence or absence of any birth defect, congenital abnormalities, or maternal and newborn complications, will be reported to the Sponsor. Any complication of pregnancy during the trial and any complication of pregnancy that the Investigator becomes aware of after withdrawal from the trial will be reported as an adverse event or serious adverse event, as appropriate.

If the pregnancy in the women participating in the trial and/or the female partners of men participating in the trial does not continue to term, one of the following actions will be taken:

- For a spontaneous abortion, report as a serious adverse event (both Pregnancy and Serious Adverse Event Forms should be completed).
- For an elective abortion due to developmental anomalies, report as a serious adverse event (both Pregnancy and Serious Adverse Event Forms should be completed).
- For an elective abortion **not** due to developmental anomalies, report on the Pregnancy Form; do not report as an adverse event.

## 8.6. Clinical Product Complaints

### 8.6.1. Definition of Clinical Product Complaints

A clinical product complaint is defined as a problem or potential problem with the physical quality or characteristics of clinical IMP supplies and/or clinical device supplies used in a clinical research trial sponsored by Teva.

A device deficiency is an inadequacy of a medical device with respect to its identity, quality, durability, reliability, safety, or performance. Device deficiencies include malfunctions, use errors, and inadequacy of the information supplied by the manufacturer.

Examples of a clinical product complaint include, but are not limited to, the following:

- suspected contamination
- questionable stability (eg, color change, flaking, crumbling)
- defective components
- missing or extra units (eg, primary container is received at the investigational center with more or less than the designated number of units inside)
- incorrect packaging or incorrect or missing labeling/labels
- unexpected or unanticipated taste or odor, or both
- device deficiency eg, any inadequacy of an investigational medical device or combination product with respect to its identity, quality, durability, reliability, usability, safety, or performance. This includes malfunctions, use errors, inadequate labeling (eg, unintelligible label, incorrect expiry date)

Each investigational center will be responsible for detecting, documenting, and reporting a clinical product complaint by completing the Product Complaint Form provided by Teva and emailing it to [[contact]](mailto:[contact]) as soon as possible after becoming aware of the issue.

Reporting a complaint must not be delayed even if not all the required information can be immediately obtained. Known information must be immediately reported. The Sponsor will collaborate with the Investigator to obtain any outstanding information.

Once the complaint has been investigated by the Sponsor, when required, an event closure letter may be sent to the investigational center where the complaint originated or to all investigational centers using the product.

If the clinical product complaint is related to a device, comparator, co-medication, rescue medication, or any other product planned in the protocol not manufactured by Teva, the complaint will be forwarded to the manufacturer/wholesaler of that product.

